Study Objective	The primary objective of this study is to provide safety data for the SMF Short Modular Femoral Stem Hip System up to a follow up period of 20 years post implantation
Primary Endpoint	Safety Data based on the following assessments: 
 ▪ Whole blood cobalt and chromium ion levels collected annually for symptomatic subjects and every 3 years for non-symptomatic subjects ▪ Metal artifact reduction sequence (MARS) magnetic resonance imaging (MRI) or Computed Tomography (CT) in subjects with whole blood cobalt and/or chromium > 7 parts per billion (ppb)
Secondary Endpoints	
 ▪ Standard of Care Radiographic assessments ▪ HOOS JR Hip Questionnaire ▪ Revision of any component of the study device for any reason ▪ Adverse events assessment
Length of Study	Approximately Twelve Years. Subjects have been implanted with the SMF Device in 2009 and 2010 at the investigational site. The Baseline visit will be determined as the first visit to site after Ethics approval for the study has been received. This will be approximately 8-9 years post implant. Enrolled subjects will be followed up to 20 years post SMF implant
Number of Sites	1 site (Australia)
Sample Size	Up to 26 subjects based on feasibility only
Inclusion Criteria	
 ▪ Subject has undergone primary total hip arthroplasty with the SMF Short modular femoral stem at the study site and still has the original implant at the time of Ethics Committee (EC) approval of the study ▪ Subject is willing and able to participate in follow-up visits at the study site

Exclusion Criteria	
 ▪ The Subject, in the opinion of the PI, has an emotional or neurological condition that would affect their ability or willingness to participate in the study including mental illness, mental retardation, drug or alcohol abuse ▪ Subject is known to be at risk for lost to follow-up or failure to return for scheduled visits
---------------------------	--

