3.0 Study Design

This is a single arm, consecutive series study to collect relevant clinical, laboratory and radiological data in up to 26 subjects, who have been implanted with the SMF Short Modular Femoral Stem THA system at 1 site in Australia.

The Baseline visit will be determined as the first visit to site after Ethics approval for the study has been received. This will be approximately 8-9 years post implant. Enrolled subjects will be followed up to 20 years post SMF implant. The Baseline visit assessments are described in Section 5.5 and 5.6. Post Baseline, the study will allow for metal ion assessments every 3 years for asymptomatic subjects and annual assessments for subjects with pain, swelling, and/or functional limitations if assessed by the Principal Investigator to be related to the SMF implant, having ruled out all other probable causes for the subject. If the subject has elevated whole blood cobalt or chromium (defined as >7ppb) a MARS MRI or CT will be obtained. These types of imaging techniques are aimed at

detecting inflammatory degenerative evolution of periarticular soft tissues including pseudo-tumors. A functional Questionnaire, HOOS JR Questionnaire will be completed at all patient site visits.

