3.1 Primary Endpoint

- Safety assessment of the SMF Short Modular Femoral Stem implanted Subjects using Metal Ion Analysis and MARS MRI/ or CT at Baseline and at protocol scheduled visits at the 1 yearly or at the 3 yearly time point as per the study schematic Table 1.

Metal Ion Level assessment

- All Subjects at Baseline and every three years afterwards will have whole blood collected for metal ion testing of whole blood cobalt and chromium
- Symptomatic subjects with pain, swelling, and/or functional limitations if assessed by the PI to be related to the implant will have whole blood collected for metal ion testing of cobalt and chromium annually

MARS MRI/CT

- Subjects with whole blood cobalt and/or chromium > 7 ppb will have MARS MRI (or CT if MRI is contraindicated) performed

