8.2.1 General

The subjects will be described and summarised using the collected baseline demographic and medical variables which include but are not limited to age, gender, ethnicity, medical and medication history, diagnostic factors.

Primary and secondary endpoints will be evaluated using listings and appropriate summary statistics. The summary statistics for both primary and secondary outcomes will be reported together with a 95% confidence interval to assess the degree of precision in the estimates.

Summary statistics for baseline data, primary and secondary endpoints will be given according to the nature of the variable, continuous or categorical. For categorical variables, the number of observations, mean, standard deviation, median, minimum, and maximum will be presented, while for categorical variables the number of observations, frequency, and percentages will be reported.

All statistical tests will be exploratory in nature as the study is not powered for any statistical testing. Appropriate parametric and/or non-parametric analyses will be chosen for statistical analysis. Test of association for the table of counts will be based on the Fisher's Exact Test unless otherwise inappropriate. The exploratory analysis of continuous variables will be done using t-test if appropriate. The Wilcoxon rank-sum test will be explored if the data is non-normal. All statistical tests will be considered at 5% significance level.

All statistical analyses and calculation of confidence intervals will be performed using SAS software.

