8.3.1 Analysis of Primary Endpoint

- Safety assessment of the SMF Short Modular Femoral Stem implanted Subjects using Metal Ion Analysis and MARS MRI/ or CT at Baseline and at protocol scheduled visits at the 1 yearly or at the 3 yearly time point as per the study schematic Table 1.

Metal Ion Level assessment

- All Subjects at Baseline and every three years afterwards will have whole blood collected for metal ion testing of whole blood cobalt and chromium
- Symptomatic subjects with pain, swelling, and/or functional limitations if assessed by the PI to be related to the implant will have whole blood collected for metal ion testing of cobalt and chromium annually

The concentration levels of cobalt and chromium will be summarized using mean, median, SD, minimum and maximum at all recorded time points for all subjects. The results will be further categorized as subjects with pain, swelling and functional limitations. An exploratory ANOVA model will be fitted to evaluate any variation in changes over time.

MARS MRI/CT

- Subjects with whole blood cobalt and/or chromium > 7 ppb will have MARS MRI (or CT if MRI is contraindicated) performed

Based on the MARS MRI/CT results, a binary variable will be used to categorize subjects with blood cobalt and/or chromium > 7 ppb or below at all recorded time points. The frequencies together with percentages will be reported. The results will be further categorized as subjects with pain, swelling and functional limitations.

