8.3.2 Analysis of Secondary Endpoints

- Revision of any component for any reason – Revision will be evaluated as the frequency of subjects with component revision at the end of study and expressed as a percentage of the full analysis set.
- Standard of Care Radiographic assessments
 - Loosening as indicated by radiolucencies > 2mm - a binary variable will be used to categorize subjects with radiolucencies > 2mm or below at all recorded time points. The frequencies together with percentages will be reported. The results will be further categorized as subjects with pain, swelling and functional limitations.
 - Evidence of surface wear or particulate debris generation as indicated by early osteolysis, implant migration, or other clinical or radiographic abnormalities such as pseudo tumors or corrosion

The presence of surface wear and all types radiographic abnormalities will be summarized as frequencies together with percentages at all recorded time points.

- HOOS JR Questionnaire
 - The score will be calculated to assess clinical efficacy

The HOOS score will be summarized using mean, median, SD, minimum and maximum at all recorded time points for all subjects. The results will be further categorized as subjects with pain, swelling and functional limitations. An exploratory t-test will be fitted to evaluate the difference between baseline and end of study scores.

- Device Related Adverse Events
 - Safety will be evaluated by assessing the frequency and nature of Device related adverse events as defined in the Safety Reporting section

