10.0 Risk – Benefit Analysis

10.1 Study Related Risks

Possible risks that may occur as a result of this study are:

- **X-Ray Exposure:** This study involves the use of x-ray evaluation. X-ray exposure is cumulative over a lifetime and total exposure should be kept to a minimum. However, if the x-ray exposure when participating in the study is equivalent to the exposure the subject would receive if they chose not to participate in the study, there is no additional risk associated with this study.
- **Loss of Confidentiality:** As a result of participating in the study there could be a risk of loss of protected subject information confidentiality. All applicable confidentiality standards and data protection and privacy laws will be followed by the Sponsor, Smith & Nephew, to ensure that data collection is handled in confidence. Data will be coded and handled only by appropriately qualified and authorized personnel.
- **Phlebotomy:** Blood draws will be required to obtain blood for metal ion assessment of cobalt chrome and chromium levels. Pain and bruising and possible infection at the site of blood draw and fainting may occur. The risk for these events will be reduced by use of approved medical equipment for blood draws and personnel trained in phlebotomy.
- **Metal artifact reduction sequence (MARS) magnetic resonance imaging (MRI)/Computerized tomography (CT):** MARS MRI will be indicated for study subjects who are symptomatic according to the Protocol. Radiologic evaluations used in this study are to be considered standard of care. There is no additional study-related radiologic exposure. The monitoring of symptomatic study subjects with MARS MRI or CT (where MRI is not recommended) will follow standard of care recommendations.

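### Section 8.3.1 analyses the MARS MRI/CT part of the primary endpoint with the blood-metal threshold that triggers the scan, so no primary variable records what the scans show

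*Combined protocol and SAP*

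**What the plan says.** The synopsis lists two primary assessments. One is whole blood cobalt and chromium; the other is "Metal artifact reduction sequence (MARS) magnetic resonance imaging (MRI) or Computed Tomography (CT) in subjects with whole blood cobalt and/or chromium" above 7 ppb. Section 3.1 repeats this and sets the rule for imaging: "Subjects with whole blood cobalt and/or chromium > 7 ppb will have MARS MRI (or CT if MRI is contraindicated) performed". Section 3.0 gives the purpose of the scans as "detecting inflammatory degenerative evolution of periarticular soft tissues including pseudo-tumors".

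Section 8.3.1 then sets out the primary analysis under two sub-headings.

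- **Metal ions:** "The concentration levels of cobalt and chromium will be summarized using mean, median, SD, minimum and maximum", with an exploratory ANOVA for change over time. No count of subjects above 7 ppb is asked for here.
- **MARS MRI/CT:** the trigger rule is restated, followed by "Based on the MARS MRI/CT results, a binary variable will be used to categorize subjects with blood cobalt and/or chromium > 7 ppb" or below, with frequencies and percentages at each recorded time point and a further split by symptoms.

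Three other places bear on scan findings.

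- Section 8.2.1: "Primary and secondary endpoints will be evaluated using listings and appropriate summary statistics".
- Section 8.3.2, under standard-of-care radiographic assessments, gives pseudo tumors as an example of an abnormality and adds: "The presence of surface wear and all types radiographic abnormalities will be summarized as frequencies together with percentages at all recorded time points".
- Section 8.2 defers detail to an SAP to be finalised before database lock.

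Section 10.1 describes the trigger differently: "MARS MRI will be indicated for study subjects who are symptomatic according to the Protocol".

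**The concern.** The sentence in 8.3.1 names the scan as the source of the variable and a blood concentration as its content. These do not fit together: a scan does not yield a cobalt or chromium level, and the level is known before the scan is ordered. The text therefore puts the condition for imaging where the imaging outcome should be.

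The study is descriptive and has no powered hypothesis, so the variables it describes are its whole output. If one of two primary components has no variable of its own, the question that the scans are meant to answer, namely how many subjects with raised ions have soft-tissue damage, has no specified primary result. Only a subset of subjects is scanned, so a percentage reported elsewhere without a stated denominator could also be read in quite different ways.

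**Working it through.** The plan states no figure to reproduce; the sample size of up to 26 rests on feasibility alone. The check is mainly one of logic, followed by an illustration.

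**Step 1: trigger and variable side by side.** Under section 3.1, a subject is scanned if cobalt and/or chromium exceeds 7 ppb. Under the MARS MRI/CT heading of 8.3.1, the variable is whether cobalt and/or chromium exceeds 7 ppb. Among subjects scanned under that rule at a given visit, the variable equals yes for every one of them, 100% by construction. Among all subjects it only dichotomises the blood result. In neither group does it depend on the scan.

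**Step 2: what the written variable reports, against what the scans could show.** Inputs: N = 26 (synopsis, taken as the number with a blood result), and k = number above 7 ppb, all scanned. The documents give no k, so 3, 8 and 13 are assumed. Let x be the number of abnormal scans, from 0 to k. The written variable is k/N; an imaging variable would be x/k. Intervals are exact (Clopper-Pearson) 95%: the lower limit is the 0.025 quantile of Beta(x, n − x + 1) and the upper limit is the 0.975 quantile of Beta(x + 1, n − x). The lower limit is 0 when x = 0 and the upper limit is 100% when x = n. For the written variable, k takes the place of x and N that of n.

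| k | Written variable k/26 | Imaging variable, no scan abnormal | Imaging variable, every scan abnormal |
|---|---|---|---|
| 3 | 11.5% (2.4 to 30.2) | 0/3 (0 to 70.8) | 3/3 (29.2 to 100) |
| 8 | 30.8% (14.3 to 51.8) | 0/8 (0 to 36.9) | 8/8 (63.1 to 100) |
| 13 | 50.0% (29.9 to 70.1) | 0/13 (0 to 24.7) | 13/13 (75.3 to 100) |

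In each row the second column stays the same for every x from 0 to k.

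**Step 3: the denominator.** Take k = 8 and x = 4. Among subjects scanned the result is 4/8 = 50.0% (15.7 to 84.3). Among all subjects it is 4/26 = 15.4% (4.4 to 34.9). The documents do not say which would be reported for a scan finding.

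**Step 4: the trigger itself.** Section 3.1 makes the scan depend on the ion level, whereas section 10.1 makes it depend on symptoms. If symptomatic subjects at or below 7 ppb were also scanned, the written variable would no longer be constant among those scanned, but it would still not be a scan result. The two sections must be reconciled, because the trigger determines who is in the denominator.

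**The case against.** The strongest reply is that imaging findings are not lost. Section 8.2.1 promises listings for all primary endpoints, and with at most 26 subjects a listing can show every scan. Section 8.3.2 summarises pseudo tumors among radiographic abnormalities, and section 10.1 calls the study's radiologic evaluations standard of care, which supports reading that item as covering MARS MRI/CT. Section 8.2.1 also asks for the number of observations and a 95% confidence interval, which would partly expose the denominator. The study has no success criterion, section 8 is described as brief, and a fuller SAP is to follow. On this view the fault is one of drafting and labelling. The illustration also uses assumed counts and estimates no bias in this study.

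Some of this stands. Scan findings may well reach the report, the intervals are illustrations only, and a confidence interval is already planned in general terms. The rest does not remove the error. Table 1 lists X-ray and MARS MRI/CT as separate rows, the secondary item does not name MARS MRI/CT, and a number of observations does not settle whether subjects scanned or all subjects form the denominator. A listing defines neither a finding nor a summary. The later SAP would inherit a rule that is wrong, not merely short of detail, and the text does not show which imaging variable was intended. The SAP need only be final before database lock in a study of about twelve years, so a scan finding left undefined until then may not be recorded consistently across visits.

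**Conclusion.** The concern holds and should be corrected. The only variable specified for the imaging component of the primary endpoint is the blood threshold that triggers the scan, so it carries no information about scan findings. This follows from the wording and needs no numerical assumption.

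The possible size depends on how many subjects exceed 7 ppb, which the documents do not give. With 3 to 13 of 26 assumed above it and all scanned, the reported figure would be fixed at between 11.5% and 50.0%, while the proportion of abnormal scans could lie anywhere from 0 to 100%. The claim is limited to the absence of a primary imaging variable; it does not say that imaging data are absent from the plan. The count above 7 ppb is useful and is specified nowhere else, but it belongs with the metal ion results.

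**What to change.** In section 8.3.1, and in the SAP that follows from it:

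1. Move the yes/no variable for cobalt and/or chromium above 7 ppb to the metal ion paragraph. Report it at each visit as number and percentage of subjects with a blood result.
2. Under MARS MRI/CT, define a binary variable from the scan report: soft-tissue abnormality, including pseudo-tumor, present or absent. State what counts as abnormal and how MRI and CT readings are combined or shown separately. Report it at each visit as number and percentage of subjects scanned, with an exact 95% CI, next to the number above 7 ppb and the number of those scanned. State that it describes the scanned subset only.
3. Reconcile the scan triggers in sections 3.1 and 10.1, since they set the denominator of item 2.

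The cost is revised wording, one extra table, a definition of an abnormal scan and possibly one CRF field for the finding; the CRFs are not among the documents, so that last item cannot be confirmed. Items 1 and 2 require no additional scans.

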6.1.7 Revisions

Subjects who have undergone a revision THA procedure to the primary SMF Short Modular Femoral stem, following the initial surgery, will be considered discontinued from the date of the revision procedure and will not receive any further study-related follow-up from this date. The End of Study CRF and Serious Device Adverse Event (SDAE) case report form will be completed to document the date of revision, adverse events and any radiographic assessment if available.

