8.0 Statistical Procedures

This is a single center, single arm, consecutive series study to evaluate the safety outcomes of hip arthroplasty with the SMF Short Modular Femoral Stem THA system. Up to 26 subjects will be enrolled in the study. The sample size was chosen based on the feasibility of recruitment only without regard for statistical power as this is a descriptive study and there is no available previous data for sample size justification.

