8.4 Hypothesis and Sample Size Calculation

The sample size was chosen based on the feasibility of recruitment only without regard for statistical power as this is a descriptive study to establish efficacy and safety data based on the selected primary outcomes. There is no available previous data or data from similar studies for sample size justification.

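### Results above 7 ppb and radiolucency > 2 mm are summarised only visit by visit, so revision linked to them would lower the later percentages, and no summary counts the distinct subjects affected

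*Combined protocol and SAP*

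**What the plan says.** For the primary endpoint, section 8.3.1 says that "a binary variable will be used to categorize subjects with blood cobalt and/or chromium > 7 ppb or below at all recorded time points", reported as frequencies and percentages. For loosening, section 8.3.2 says that "a binary variable will be used to categorize subjects with radiolucencies > 2mm or below at all recorded time points", again as frequencies and percentages.

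Four other provisions bear on how these figures behave over time:

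- **Revision ends follow-up.** Under section 6.1.7 a revised subject "will be considered discontinued from the date of the revision procedure", with no study follow-up after that.
- **No imputation.** Section 8.5 plans none.
- **Revision itself is handled cumulatively.** Section 8.3.2 reports subjects revised by the end of study as a percentage of a fixed set. That set is called the full analysis set, which section 8.1 does not define.
- **Other reporting.** Section 8.2.1 promises listings, and says that summary statistics "will be reported together with a 95% confidence interval to assess the degree of precision in the estimates". Section 8.5 promises an accountability report covering loss, death, revision and withdrawal.

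The synopsis gives the objective as safety data "up to a follow up period of 20 years post implantation". No section plans an ever-exceeded count, a worst value, a cumulative incidence or a time-to-event analysis for the ion threshold or for radiolucency.

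**The concern.** A percentage at a visit describes the subjects measured at that visit. Section 1.0 gives the sponsor's view that patients with the modular neck may be at greater risk of revision. If revision happens more often in subjects with high ions or loosening, those subjects leave both the numerator and the denominator of every later visit. The final-visit figure then looks better the more of them have been revised.

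The earlier visits still contain these subjects, but the series does not show how many different people were affected. One person can be above the threshold at several visits, or move in and out. For example, two subjects above 7 ppb at each of five visits could be the same two people throughout, or up to 5 × 2 = 10 different people. What is at stake is whether the report contains a summary figure, with its interval, for the number of enrolled subjects in whom the safety signal was ever seen.

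**Working it through.** **What there is to reproduce.** There is no stated rate, event count or power. Section 8.0 says "Up to 26 subjects will be enrolled in the study", and section 8.4 says "The sample size was chosen based on the feasibility of recruitment only without regard for statistical power". The documents give no ion, revision or loss rates, so every rate or count below other than the 26 is an assumption.

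**Step 1: reading the sections together.** Status is summarised by visit (8.3.1, 8.3.2), revised subjects stop being measured (6.1.7), and nothing replaces the missing values (8.5). Section 8.3.1 does not state the visit denominator. That it consists of subjects measured at the visit is an inference from 6.1.7 and 8.5.

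**Step 2: arithmetic on 26 subjects.** Let E be the number ever seen above 7 ppb, R the number of those later revised, and L the number otherwise lost, of whom Lₑ had exceeded. Exceedance is taken to persist.

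- Subject-level result: E / 26.
- Final-visit result: (E − R − Lₑ) / (26 − R − L).
- Exact 95% CI for x of n (Clopper-Pearson): lower limit is the 0.025 quantile of Beta(x, n − x + 1), upper limit is the 0.975 quantile of Beta(x + 1, n − x). The lower limit is 0 when x = 0.

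With E = 6, the subject-level result is 6/26 = 23.1% (9.0 to 43.6) in every row:

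| Exits among the 26 | Final-visit figure | Exact 95% CI |
|---|---|---|
| None | 6/26 = 23.1% | 9.0 to 43.6 |
| 2 of the 6 revised | 4/24 = 16.7% | 4.7 to 37.4 |
| 4 of the 6 revised | 2/22 = 9.1% | 1.1 to 29.2 |
| 4 revised; 1 exceeder and 4 others lost | 1/17 = 5.9% | 0.1 to 28.7 |
| All 6 revised | 0/20 = 0% | 0 to 16.8 |

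**Step 3: a range of assumed rates.** This simulation has visits at 0, 3, 6, 9 and 11.5 years after Baseline, 5–10% above 7 ppb at Baseline, 2–4% per year newly exceeding, 2–5% per year lost independently of ion level, and persistent exceedance:

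| Revision rate after exceeding | Final-visit percentage | Ever observed above, of all enrolled |
|---|---|---|
| 30% per year | about 7–13% | 14–29% |
| 10% per year | about 15–28% | 17–35% |
| None | about 25–43% | 19–39% |

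The last row matters. Without revision, unrelated loss does not lower the visit percentage. It does lower the count over all enrolled, because a lost subject can no longer be seen to exceed.

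**Step 4: how much of the gap is due to removal.** A second simulation used fluctuating levels (median 2 ppb, log SD 0.9 between and 0.35 within subjects, 3% rise per year, visits at 0, 3, 6, 9 and 12 years). The final-visit percentage against the percentage ever above was:

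- 17.7% against 24.9% with no revision;
- 11.5% against 25.0% if a quarter of those above 7 ppb are revised before the next visit;
- 7.5% against 24.9% if half are.

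So 24.9 − 17.7 = 7.2 points of the gap exist with nobody revised. They arise because an ever measure also counts temporary crossings. The part due to revision is 17.7 − 11.5 = 6.2 points and 17.7 − 7.5 = 10.2 points respectively. With 10% unrelated loss per interval and no revision, the visit figure stays at 17.8%, while the ever-observed figure falls to 21.5%.

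**The case against.** The strongest reply is that the report would not hide the problem. Revisions appear as a percentage of a fixed set: with four revised, and taking that set as all 26, the report would show 4/26 = 15.4%. The accountability report lists exits, earlier visits keep the subjects who later leave, and with at most 26 subjects a reader could count exceeders from the listings. Section 8.2 also calls the text a brief description and promises a more detailed SAP. All of this stands, and it limits the point. A reader might infer that selective exit would be invisible. The documents do not support that. What is missing is a planned summary with an interval.

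Three other strong readings are tempting:

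- **That subjects lost to follow-up also make the visit percentages look better.** Loss does so only if it is related to ion level or loosening. Unrelated loss leaves the visit figure unchanged and instead lowers an ever-observed count.
- **That the plan fails its objective.** The objective is to provide safety data in a descriptive study, and no cumulative quantity is promised.
- **That the plan should give the share exceeding 7 ppb by 20 years after implantation.** It cannot. Measurement starts about 8–9 years after implant (3.0), and only subjects with the original implant in place are eligible (5.3).

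It is also fair to say that the documents tie > 7 ppb to imaging, not to revision. The link between high ions and revision is a condition of the concern, not a finding.

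**Conclusion.** The point holds as a conditional one. If revision is linked to high ions or loosening, the planned visit percentages understate later how many subjects were affected, and no planned summary gives the number of distinct subjects. In the illustration, 23.1% of subjects affected could appear at the final visit as 9.1% or 0%. The size depends wholly on assumed counts and rates, on the inferred visit denominator and, in the 26-subject arithmetic, on exceedance persisting. Part of any gap between an ever figure and a final-visit figure arises without revision. This is a worthwhile and cheap improvement to the SAP. It does not show that the study cannot deliver safety data.

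**What to change.** Keep the per-visit percentages and state the denominator at each visit. Add to section 8.3.1 or the SAP:

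- For cobalt, chromium and either metal, the number and percentage of enrolled subjects observed above 7 ppb at any common scheduled visit from Baseline to end of study, with an exact 95% CI. The common visits are Baseline, +3, +6 and +9 years, and end of study. Using them avoids giving symptomatic subjects, who are tested annually, more chances to exceed.
- The number already above 7 ppb at Baseline.
- The numbers revised, dead or lost before any exceedance, with a note that the count is a lower bound when subjects are lost.
- A description of the result as exceedance observed from Baseline, about 8–9 years post implant, among subjects unrevised at entry.

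Report the same for radiolucency > 2 mm, using the available standard-of-care radiographs, whose timing may not match the common visits. A cumulative-incidence estimate with revision and death as competing events is optional at this sample size.

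The cost is SAP wording and one extra table per endpoint from data already collected. The drawbacks are wide intervals (9.0 to 43.6% for 6 of 26) and a measure that counts temporary crossings and depends on the number of tests.
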